11.5 Overall Response, GI Response, and GvHD VGPR

At the visits indicated in [Table 1](#), the investigator will assess the subject for overall and GI response, as well as GvHD VGPR, which are defined in the following sections:

- Overall response: Section [8.4.1](#)
- GI response: Section [8.4.2.1](#)
- GvHD VGPR ²³: Section [8.4.3](#)

11.6 Chronic GvHD Assessment

At screening and Days 100, 180 and 365, the investigator will assess the subject for chronic GvHD and acute/chronic GvHD overlap syndrome, based on the investigator's standard practice. The investigator will record the assessment in the eCRF.

11.7 Pharmacokinetic, Biomarker and Stool Sample Collection

Samples of whole blood will be obtained in a 10-mL Vacutainer[®] containing heparin anticoagulant for the determination of A₁PI and selected metabolites, as well as biomarkers, in human plasma. Blood samples will be obtained prior to the first study treatment administration and at the visits and times indicated in [Table 2](#). If study treatment is administered peripherally (Section [8.7.2](#)), the PK samples should be taken from the opposite arm as the study treatment administration, if possible. If study treatment is administered via a central indwelling catheter, the PK samples may be taken from the same infusion line if the infusion line is flushed prior to collection of the sample and the first 3 mL of blood is discarded.

Stool samples will be collected for assessment of A₁PI levels and clearance and calprotectin concentrations. One sample will be collected prior to the first dose of study treatment (either during screening or on Day 0 prior to the start of study treatment administration). A stool sample will also be collected during the 24-hour period after initiation of study treatment on Days 0 and 12 and during the 24-hour period on Days 28 and 56. The Day 28 stool sample must be collected prior to the start of study treatment administration. For inpatient visits, stool samples will be collected at the site. For outpatient visits, the sample can be collected at the site or can be collected at home and returned to the study site.

Refer to the Laboratory Manual for details of sample volumes and handling.

The following information will be captured for blood and stool sample collection in each subject's eCRF:

1. Subject's SIC
2. Time and date of start of previous study treatment infusion
3. Time and date of each blood and stool sample collected
4. Time and date of subject's most recent ingestion of food prior to sample collection (blood sample only)
5. Whether the blood sample was collected through a central or peripheral line
6. If the blood sample was collected through a peripheral line, whether it was collected through the same arm or the opposite arm, as the study treatment administration

Biomarkers to be assessed in Parts 1 and 2 include cytokines IL-2, IL-6, IL-8, and IL-10; IL-1RA; T cell subpopulations, including CD4⁺ CD25⁺ CD127⁺ FoxP3⁺ Tregs; and stool calprotectin concentrations; in Part 2 only, the following biomarkers will also be assessed: Reg3α, ST2, and TNFR1. The cytokines will be measured by enzyme-linked immunosorbent assay. The T cells will be measured using epigenetic cell counting.

11.8 Functional Assessment of Cancer Therapy – Bone Marrow Transplant

Quality-of-life will be assessed with the FACT-BMT at the visits indicated in [Table 1](#). The FACT-BMT is a 37-item scale comprised of a general core questionnaire, the FACT-G, which evaluates the health-related QoL of subjects receiving treatment for cancer, and a specific module, BMT Concerns, that addresses disease and treatment-related questions specific to BMT. The FACT-G core questionnaire assesses 4 domains:

Physical Well-being, Social/Family Well-being, Emotional Well-being and Functional Well-being. Each domain can be scored, with higher scores indicating better functioning.

The FACT-BMT, Chronic GvHD Symptom Scale and EQ-5D-5L should be collected before any other assessments are performed at the visit.

11.9 Chronic GvHD Symptom Scale

Symptoms of GvHD will be assessed with the Chronic GvHD Symptom Scale at the visits indicated in [Table 1](#). The Chronic GvHD Symptom Scale is a 30-item validated scale that measures the extent to which the subject is bothered by chronic GVHD symptoms in the following domains: skin, energy, lung, nutrition, psychological, eye and mouth. Responses are captured on a 5-point Likert scale (“no symptoms, or not bothered at all,” “slightly bothered,” “moderately bothered,” “bothered quite a bit” or “extremely bothered”). Scores for each domain are converted to a 0 to 100 scale, with higher scores indicating a greater degree to which the subject is bothered by the symptoms.

Although the scale collects chronic GvHD symptoms, several of the domains are also applicable to acute GvHD. There is no validated symptom scale that is specific to acute GvHD.

The FACT-BMT, Chronic GvHD Symptom Scale and EQ-5D-5L should be collected before any other assessments are performed at the visit.

11.10 European Quality of Life – 5 Dimensions – 5 Level

Health utility will be assessed with the EQ-5D-5L³⁰ instrument at the visits indicated in [Table 1](#). The EQ-5D-5L is a standardized subject-administered measure of health-related QoL states consisting of 5 dimensions (mobility, self-care, usual activities, pain/discomfort and anxiety/depression) each of which can take 1 of 5 responses. The responses record 5 levels of severity (no problems/slight problems/moderate problems/severe problems/extreme problems) within a particular EQ-5D dimension.

The FACT-BMT, Chronic GvHD Symptom Scale and EQ-5D-5L should be collected before any other assessments are performed at the visit.

11.11 Healthcare Resource Utilization

Healthcare resource utilization information will be recorded by the subject in the subject diary (Section 10.5) and by the investigator in the eCRF. The investigator will record the date of hospital discharge in the eCRF for the hospitalization that was ongoing at the time of the initiation of study treatment. In the subject diary, the subject will record the number and length of stay (in days) of: emergency room visits, hospital stays, intensive care admissions and urgent care center visits. After reviewing the subject diary with the subject, the investigator will enter the healthcare resource utilization data in the eCRF at the visits indicated in Table 1. These data will be collected to assess the economic impact of treatment with GLASSIA.

11.12 Mortality and Survival Assessments

All-cause, transplant-related, infection-related and GvHD-related mortality will be calculated as the time from HSCT to death; the cause of death will be based on the investigator's assessment. The date and cause of death, if applicable, will be collected in the eCRF at the visits indicated in Table 1. The following definitions will be used by the investigator to assess the cause of death. These categories are not mutually exclusive, and the investigator will select all applicable categories:

- Transplant-related mortality: death related to transplantation (including deaths related to GvHD)
- Infection-related mortality: death related to infection (including infections related to HSCT)
- GvHD-related mortality: death related to GvHD
- Other cause: any death not related to transplant, infection or GvHD

Failure-free survival, GvHD-free survival and overall survival will be collected in the eCRF at the visits indicated in Table 1.

Failure-free survival is determined by the investigator and defined as the absence of all 3 of the following criteria:

- Need for second-line treatment for acute GvHD
Second-line treatment is defined as any additional systemic treatment used for steroid nonresponsive treatment of acute GvHD. Methylprednisolone (or equivalent steroid) doses greater than 2 mg/kg/day required for the treatment of GvHD will also be considered second-line therapy

- Non-relapse mortality
Non-relapse mortality is defined as death during continuous complete remission
- Recurrent malignancy

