8.2 Overall Study Design

The overall study design is illustrated in [Figure 1](#) (Part 1) and [Figure 2](#) (Part 2).

For Parts 1 and 2, screening for eligibility will occur from Days -2 to -1. After screening, subjects will undergo the baseline visit, which is also Day 0.

Subjects will complete study visits either as inpatient or outpatient visits, in accordance with institutional practice. Following the first 2 weeks of every other day study treatment (GLASSIA in Part 1; GLASSIA or control in Part 2), subjects will undergo visits on the following days to have study treatment administered (through Day 49) and to perform safety follow-up and study procedures: Days 14, 21, 28, 35, 42, 49 and 56.

All subjects will be treated with study treatment in combination with conventional steroid treatment through Day 49, or until treatment failure, withdrawal from treatment or withdrawal from the study, whichever comes first. Thereafter, subjects will be treated with standard-of-care for the remainder of their participation in the study based on the investigator's discretion. Subjects who are withdrawn from study treatment will continue to be followed through at least Day 28 (refer to Section 10.6), unless the subject withdraws consent.

Steroid treatment after Day 49 will be at the investigator's discretion. Subjects will visit the site for follow-up visits on Days 56, 100, 180 and 365. In the event that it is not feasible for the subject to visit the site at Day 365, the visit may be conducted with a phone call.

Subjects will also receive standard antibiotic, antifungal and antiviral prophylactic treatment through Day 180 or per institutional guidelines.

Assessments of vital signs, clinical laboratory data (hematology and chemistry), local tolerability and AEs will be performed throughout the study.

Steroid Taper

Tapering of steroids may commence after a subject responds to therapy (overall response, also referred to as GvHD response, as defined in Section 8.4.1); however, the dose of steroid should not be tapered below 2 mg/kg/day (methylprednisolone or equivalent dose) before Day 2 or below 0.25 mg/kg/day (methylprednisolone or equivalent dose) before Day 28.

Subjects who discontinue study treatment (GLASSIA or control) will be treated with standard-of-care for the remainder of their participation in the study.

Treatment Failures

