8.4.2 Secondary Outcome Measures

8.4.2.1 Efficacy (Parts 1 and 2)

Key Secondary Efficacy Outcome Measures

1. Proportion of subjects achieving GI response at Day 28. Gastrointestinal response is defined as GI CR + PR, which are defined as follows:
 - GI CR is defined as
 - a) Able to eat; not requiring parenteral nutrition, and
 - b) Passing primarily formed stools
 - GI PR is defined as
 - a) Decrease in need for parenteral nutrition to $\leq 50\%$ of required calories; and
 - b) Reduction of stool volume by $\geq 50\%$, without ileus

Other Secondary Efficacy Outcome Measures

1. Proportion of subjects achieving overall response at Day 56
2. Change from baseline in acute GvHD grading at Days 28, 56 and 180
3. Incidence of chronic GvHD at Days 100, 180 and 365

4. Duration of any overall response
5. Duration of any GI response
6. Overall survival through Days 100, 180 and 365
7. Transplant-related mortality at Days 28, 56, 100 and 180
8. Failure-free survival at Days 100 and 180
9. GvHD-free survival at Days 28, 56, 100 and 180
10. Infection-related mortality at Days 28, 56, 100 and 180
11. GvHD-related mortality at Days 28, 56, 100 and 180
12. All-cause mortality at Days 28, 56, 100 and 180

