9. SUBJECT SELECTION, WITHDRAWAL, AND DISCONTINUATION

9.1 Inclusion Criteria

Subjects who meet **ALL** of the following criteria are eligible for Parts 1 and 2 of this study:

1. Male or female subjects aged ≥ 18 years at the time of screening
2. Recipient of an HSCT
3. The disease indication for which the subject required HSCT must be in remission
4. Newly diagnosed acute GvHD, including lower GI involvement (modified International Bone Marrow Transplant Registry [IBMTR] Severity Stage 1 to 4 [>500 mL diarrhea/day]), with or without other organ system involvement.
5. Willing to undergo or must have had a lower GI biopsy within 7 days of informed consent to confirm GI GvHD. Biopsy results are not needed to initiate treatment; however, if biopsy results are not consistent with aGvHD, treatment with GLASSIA will be discontinued.
6. Subjects must be receiving systemic corticosteroids. Treatment with methylprednisolone/systemic steroids must have been initiated within 72 hours prior to the first dose of study treatment after enrollment.
7. Evidence of myeloid engraftment (absolute neutrophil count $\geq 0.5 \times 10^9/L$)
8. Lower GI GvHD manifested by diarrhea must have other causes of diarrhea ruled out (eg, negative for *Clostridium difficile* or cytomegalovirus [CMV] infection or oral magnesium administration)
9. Karnofsky Performance Score $\geq 50\%$ ²⁹
10. If female of childbearing potential, subject presents with a negative blood pregnancy test
11. Females of childbearing potential with a fertile male sexual partner must agree to employ adequate contraception for the duration of the study. Adequate contraception is defined as using hormonal contraceptives or an intrauterine device combined with at least 1 of the following forms of contraception: a diaphragm, cervical cap or a condom
12. Males must use adequate contraception and must not donate sperm for the duration of the study. Adequate contraception for the male subject and his female partner is defined as using hormonal contraceptives or an intrauterine device combined with at least 1 of the following forms of contraception: a diaphragm, cervical cap or a condom
13. Subject is willing and able to comply with the requirements of the protocol

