13.4.2 Secondary Outcome Measures

Part 1

The secondary efficacy outcome measures (see Section 8.4.2.1) and the secondary PK outcome measures (see Section 8.4.2.3) will be summarized with descriptive statistics. PK parameters will be summarized with the mean, SD, median, minimum and maximum values, geometric mean and percentage of coefficient of variation.

Part 2

The key secondary endpoint of GI response rate at Day 28 (see Section 8.4.2.1) and all binary types of endpoints, including overall response at Day 56, will be analyzed similarly to the overall response rate at Day 28.

Other secondary endpoints that will be derived in the statistical analyses include, but are not limited to, the following:

- All-cause, transplant-related, infection-related and GvHD-related mortality: defined as the time from HSCT to death due to any cause, transplantation, infection and GvHD, respectively
- Duration of any overall and GI response

The secondary endpoints of overall survival and failure-free survival rate at different timepoints will be analyzed using the Cox proportional hazard model. The hazard ratio (and the corresponding 95% confidence interval) will be reported. A Kaplan-Meier plot will also be presented. All-cause, transplant-related, infection-related and GvHD-related mortality will be analyzed using a similar method with competing-risk taken into consideration.

The other time-to-event types of secondary endpoints, including duration of any overall response and any GI response, will also be analyzed using the Cox proportional hazard model and summarized using Kaplan-Meier plots.

The change from baseline in acute GvHD grading will be analyzed with a shift table.

All other secondary efficacy endpoints will be summarized with descriptive statistics.

Safety Analyses (Parts 1 and 2)

Secondary safety outcome measures will be summarized with descriptive statistics and qualitative analysis (see Section 8.4.2.2). Adverse events will be listed for each subject and summarized by system organ class and preferred term by using the Medical Dictionary for Regulatory Activities. Safety laboratory data, vital signs measurements and biomarker data will be listed for each subject and summarized with descriptive statistics by treatment group (Part 2 only), visit and assessment time.

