20.2 Schedule of Study Procedures and Assessments

Table 1 Schedule of Study Procedures and Assessments (Parts 1 and 2)																		
	Scr	Treatment Period														No Study Treatment Follow-Up		
Study Day	-2 to -1	Baseline/ day 0	2	4	6	8	10	12	14	21	28 ^a	35	42	49	56	100	180	365 ^b
Visit window (± days)		1	1	1	1	1	1	1	1	1	1	1	1	1	1	5	5	5
Informed consent ^c	X																	
Inclusion/exclusion criteria	X																	
Demographics	X																	
Medical, surgical and transplant history	X																	
Medication history	X																	
Randomization (Part 2 only)		X																
Subject diary	X									X	X	X	X	X	X			
FACT-BMT, Chronic GvHD Symptom Scale, EQ-5D-5L ^d		X									X				X	X	X	X
Physical examination	X				X				X		X				X			
Vital signs ^e	X				X				X		X				X			
12-lead ECG	X																	
CMV testing	X				X				X	X	X	X	X	X	X	X	X	
HIV testing ^{f,g}	X																	
Clinical laboratory tests ^e	X		X	X	X			X	X		X				X			
Serum pregnancy test ^h	X														X			
Lower GI biopsy ⁱ	X																	
Biomarker sample collection ^e		X			X				X		X							
GvHD staging/assessment	X	X	X	X	X	X	X	X	X	X	X	X	X	X	X	X	X	

Table 1 Schedule of Study Procedures and Assessments (Parts 1 and 2)																		
	Scr	Treatment Period														No Study Treatment Follow-Up		
Study Day	-2 to -1	Baseline/ day 0	2	4	6	8	10	12	14	21	28 ^a	35	42	49	56	100	180	365 ^b
Visit window (± days)		1	1	1	1	1	1	1	1	1	1	1	1	1	1	5	5	5
Overall response, GI response and GvHD VGPR		X	X	X	X	X	X	X	X	X	X	X	X	X	X	X	X	
Chronic GvHD assessment	X															X	X	X
Cumulative dose of steroids											X				X	X	X	
PK sample collection ^g		X ---> X						X ---> X	X	X				X ---> X				
Assessment of recurrent malignancy	X ----- > X																	
Adverse events	X ----- > X																	
Medications and non-drug therapies ⁱ	X	X ----- > X																
Mortality and survival assessments ^k											X				X	X	X	X
Study treatment administration ^l		X	X	X	X	X	X	X	X	X	X	X	X	X				
Administration of steroid treatment ^{l,m}	X	X ----->	X															
Viral prophylaxis ⁿ	X	X ----->	X															
Stool sample collection ^g	X	X						X			X				X			

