22. SUMMARY OF CHANGES

Protocol 471501: Amendment 1 2017 APR 19

Replaces: Original: 2016 APR 19

In this section, changes from the previous version of the Protocol, dated 2016 APR 19, are described and their rationale is given.

1. Throughout the document
Description of Change: Minor grammatical and/or administrative changes have been made.
Purpose for Change: To improve the readability and/or clarity of the protocol.
2. Throughout the document
Description of Change: NCT Number added.
Purpose for Change: NCT Number provided has been obtained.
3. Throughout the document
Description of Change: IND Number added.
Purpose for Change: IND Number provided has been obtained.
4. Section 1 Study Personnel; Investigator Acknowledgement Signature Pages
Description of Change: Name of Signatory has been changed.
Purpose for Change: Sponsor Authorized Representative has changed.
5. Section 3 Synopsis and throughout document
Description of Change: Change Study Day 1 to Baseline/Day 0; all subsequent days for dosing/follow-up are in reference to the Baseline; changed Study Days 1, 3, 5, 7, 9, 11, 13, 15, 22, 36, 43, and 50 to Baseline/Day 0 and Days 2, 4, 6, 8, 10, 12, 14, 21, 35, 42, and 49.
Purpose for Change: To correct an error in calculating dosing schedule.
6. Section 3 Synopsis (Primary Objective); Section 7.2 Primary Objective
Description of Change: Change “treatment response at 28 days” to “treatment response at Day 28”.
Purpose for Change: Day 28 is a planned study visit and it’s actually on the 29th day of treatment.

7. Section 3 Synopsis (Exploratory Objectives #3; Pharmacodynamics assessment #3); Section 7.4 Exploratory Objectives (Parts 1 and 2); Section 8.4.3 Exploratory Outcome Measures; Section 11.7 Pharmacokinetic, Biomarker and Stool Sample Collection; Section 20.3 Clinical Laboratory Assessments (Table 2 footnote i)
Description of Change: Deleted IL-32 and heparin sulfate.
Purpose for Change: There is no validated assay for these analyses.
8. Section 3 Synopsis (Exploratory Objectives #3; Pharmacodynamics assessment #3); Section 7.4 Exploratory Objectives (Parts 1 and 2); Section 8.4.3 Exploratory Outcome Measures; Section 11.7 Pharmacokinetic, Biomarker and Stool Sample Collection; Section 20.3 Clinical Laboratory Assessments (Table 2 footnote i)
Description of Change: Deleted Reg3 α , ST2, and TNFR1 from Parts 1 and 2 and added these under new heading/text for Part 2 Only.

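### Part 2 mortality is defined as time from transplant, but Days 28, 56, 100 and 180 at which it is reported are study days counted from baseline

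*Protocol*

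**What the plan says.** **Definition.** Protocol Section 11.12, which is not limited to one part, says: "All-cause, transplant-related, infection-related and GvHD-related mortality will be calculated as the time from HSCT to death". Section 13.4.2, under Part 2, says the four mortality endpoints are "defined as the time from HSCT to death due to any cause, transplantation, infection and GvHD, respectively". It adds that they "will be analyzed using a similar method with competing-risk taken into consideration", where the similar method is the Cox model with Kaplan-Meier plots used for overall and failure-free survival.

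**Reporting times.** Section 8.4.2.1 lists "All-cause mortality at Days 28, 56, 100 and 180", and gives the same four days for transplant-related, infection-related and GvHD-related mortality.

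**Day count.** Section 8.2 says: "After screening, subjects will undergo the baseline visit, which is also Day 0". In Section 20.2, Table 1, the row "Mortality and survival assessments" is marked at study Days 28, 56, 100, 180 and 365. Item 5 of the summary of changes describes the convention now in force: "all subsequent days for dosing/follow-up are in reference to the Baseline".

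**Entry.** Section 9.1 requires a transplant, "Evidence of myeloid engraftment" and newly diagnosed acute GvHD.

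**Other survival endpoints.** The protocol gives no time origin for overall, failure-free or GvHD-free survival.

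**SAP.** SAP Section 7.2.2 counts overall survival, cause-specific mortality, failure-free survival and GvHD-free survival from first dose, and treats all-cause mortality as the complement of overall survival. SAP Section 1 limits the SAP to Part 1 and says that no SAP will be written for Part 2.

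**The concern.** The defined variable and the reported endpoint run on different clocks. A subject's baseline falls some weeks after transplant, and the subject must be alive throughout that interval to be enrolled. If time is counted from transplant without delayed entry, the interval is immortal time, and every landmark is reached before the matching study visit.

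Three consequences follow for an analyst who programs Part 2 as written:

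- Mortality read off a Kaplan-Meier or cumulative-incidence curve at a labelled day is too low, in both arms.
- A subject who enters 28 or more days after transplant cannot count as a Day 28 death.
- All-cause mortality at Days 100 and 180 is not 1 minus overall survival if overall survival is counted from baseline.

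At stake are the landmark rates and curves of four secondary endpoints. The randomised comparison of hazards is not at stake.

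**Working it through.** **1. Comparing the texts.** No mortality rate, event count or power figure in the documents depends on the time origin, so there is no plan figure to reproduce.

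| Item | Where | Clock |
|---|---|---|
| Definition of the four mortality endpoints | Protocol 11.12; 13.4.2 (Part 2) | Transplant |
| Days 28, 56, 100 and 180 | Protocol 8.4.2.1 with 8.2 and Table 1 | Baseline = Day 0 |
| Same endpoints, Part 1 | SAP 7.2.2 | First dose |
| Rule linking the clocks, or delayed entry | None found | – |

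The list in Section 8.4.2.1 that holds the mortality endpoints also has change from baseline in GvHD grading at Days 28, 56 and 180, which can only be study days.

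**2. Assumed inputs.** The documents give no transplant-to-baseline lag. They give mortality only as background: up to 70% to 80% in severe GI GvHD with no time horizon (Section 6.2), and 6 of 12 steroid-refractory subjects alive at follow-up of up to 820 days (Section 6.4.2). The illustration therefore assumes:

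- mortality M at study Day 180 of 30%, 50% or 70%, with 80% as an extreme;
- a lag L of 20 to 60 days;
- a constant hazard after baseline.

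**3. Formulas.** λ = −ln(1 − M)/180.

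- Study clock: F(d) = 1 − exp(−λd).
- Transplant clock without delayed entry: F(max(0, d − L)).

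**4. Example with M = 50%.** λ = 0.6931/180 = 0.003851 per day.

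- Day 28, study clock: 1 − exp(−0.003851 × 28) = 10.2%. With L = 20, only 8 days count: 1 − exp(−0.003851 × 8) = 3.0%. With L = 60 the result is 0%.
- Day 180, study clock: 50.0%. With L = 20: 1 − exp(−0.003851 × 160) = 46.0%. With L = 60: 1 − exp(−0.003851 × 120) = 37.0%.

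**5. Results.** Each cell gives the study clock, then the transplant clock for L = 60 to L = 20.

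| M | Day 28 | Day 56 | Day 100 | Day 180 |
|---|---|---|---|---|
| 30% | 5.4% vs 0–1.6% | 10.5% vs 0–6.9% | 18.0% vs 7.6–14.7% | 30.0% vs 21.2–27.2% |
| 50% | 10.2% vs 0–3.0% | 19.4% vs 0–12.9% | 32.0% vs 14.3–26.5% | 50.0% vs 37.0–46.0% |
| 70% | 17.1% vs 0–5.2% | 31.2% vs 0–21.4% | 48.8% vs 23.5–41.4% | 70.0% vs 55.2–65.7% |
| 80% | 22.1% vs 0–6.9% | 39.4% vs 0–27.5% | 59.1% vs 30.1–51.1% | 80.0% vs 65.8–76.1% |

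For M from 30% to 70%, the Day 180 rate falls by between 30.0 − 27.2 = 2.8 points and 70.0 − 55.2 = 14.8 points.

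**6. Cause-specific incidence.** Assume that 60% of deaths are transplant-related, M = 50%, and the lag is uniform on 20 to 60 days. Incidence is 0.6 × F, with F averaged over the lag on the transplant clock. Day 28: 6.1% against 0.2%. Day 180: 30.0% against 25.0%.

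**7. Treatment comparison.** 2,000 trials were simulated per scenario: 74 per arm, constant cause-specific hazards, the same 60% share (control arm) and lag, a hazard ratio of 0.55 for transplant-related death and 1 for other deaths, and follow-up to study Day 180. Power is at one-sided 2.5% for the cause-specific Cox model. Values are study clock vs transplant clock.

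| Control mortality | Cause-specific HR | Power | Subdistribution HR |
|---|---|---|---|
| 30% | 0.539 vs 0.540 | 23.3% vs 23.3% | 0.541 vs 0.541 |
| 50% | 0.548 vs 0.548 | 38.0% vs 37.3% | 0.553 vs 0.553 |
| 70% | 0.539 vs 0.540 | 56.1% vs 55.3% | 0.550 vs 0.550 |

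The choice of clock moves the rates and leaves the hazard ratio essentially alone.

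**The case against.** The strongest reply is that the documents never say which clock was meant. The transplant origin appears in two sections, so it does not look like a slip, and Section 8.4.4 speaks of mortality up to 2 years after transplant. On that view the protocol could keep the transplant clock with left truncation and relabelled days. But Section 8.4.4 gives background from cited studies, and the protocol provides neither left truncation nor relabelling. A transplant-clock analysis is legitimate only with both.

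A second reply is that mortality at Day 28 could mean the proportion dead by that visit, with the transplant-origin variable used only in the Cox model. The understated rates do need someone to read the landmark off the transplant-clock curve. However, the visit-proportion reading is written nowhere, and it fits poorly with the time-to-event and competing-risk method of Section 13.4.2.

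Several points stand:

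- Item 5 of the summary of changes is weak support, because the days it renumbers do not include 28, 56, 100 or 180. Section 8.2 and Table 1 carry the argument without it.
- The lag, the mortality rates, the 60% share and the hazard ratio of 0.55 are assumptions. For the last two, only single values were tried.
- The treatment comparison is not harmed. An all-cause Cox check with declining hazards (Weibull shape 0.4 to 1.0) and lags up to 120 days moved the hazard ratio by at most 0.006 and power by at most about 2 points.
- The Part 1 SAP already uses the study clock. It does not govern Part 2, but it shows how the sponsor put the same endpoints into practice, and so supports the correction.

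**Conclusion.** The concern holds, as a minor point. As written, the Part 2 definition does not yield the endpoint that the protocol lists, and used literally it understates mortality at every labelled day. Under a constant hazard, 30% to 70% mortality at study Day 180 and a lag of 20 to 60 days, the shortfall at Day 180 is 2.8 to 14.8 points, and most or all of the Day 28 mortality disappears. The direction needs only that baseline follows transplant; the size rests wholly on the assumed lag, mortality and hazard shape.

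The effect is confined to the landmark rates and curves of four secondary endpoints. Section 11.12 has the same wording for Part 1, but the SAP resolves it there by counting from first dose. No result was affected, because the study was terminated before Part 2 began.

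**What to change.** In Protocol Sections 11.12 and 13.4.2:

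- Replace the transplant origin with randomisation for Part 2 and first dose for Part 1 (as in the SAP), for all four mortality endpoints.
- State the same origin for overall, failure-free and GvHD-free survival.
- Report all-cause mortality as 1 minus overall survival.
- If an analysis from transplant is wanted, make it supplementary, with delayed entry at randomisation or first dose and time points labelled as days after transplant.

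The cost is two or three sentences. No new data are needed: the transplant date (Section 11.1), the date of death (Section 11.12) and the randomisation and dosing dates are already collected.
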